CFSE	Carboxyfluorescein succinimidyl ester, a fluorescent cell staining dye
CRFs	Case Report Forms
CRR	Continuing review report
CTC	WRAIR Clinical Trials Center
DAIDS	Division of AIDS
DODI	Department of Defense Instruction
DSMB	Data Safety Monitoring Board
eCRF	Electronic Case Report Forms
EDC	Electronic Data Capture
EDTA	Ethylenediaminetetraacetic acid
ELISPOT	Enzyme-Linked Immunospot
FDA	U.S. Food and Drug Administration
FSH	Follicle stimulating hormone
GBS	Guillain-Barré syndrome
GCLP	Good Clinical Laboratory Practices
GCP	Good Clinical Practices
HAE	Hereditary angioedema
HBsAg	Hepatitis B surface antigen
HIV-1	Human Immunodeficiency Virus 1
HRT	Hormonal replacement therapy
HSPB	Human Subjects Protection Branch, WRAIR
IBs	Investigational brochures
ICH	International Conference on Harmonization
ICS	Intra-cellular cytokine staining
ID	Infectious disease

Abbreviation or Specialist Term	Explanation
IEC	Independent Ethics Committee
IFN γ	Interferon gamma
IgA	Immunoglobulin A
IgG	Immunoglobulin G
IL2	Interleukin 2
IM	Intramuscular
IND	Investigational New Drug
IP	Investigational product
IQR	Interquartile range
IRB	Institutional Review Board
ISM	Sponsor Independent Safety Monitor
IUD	Intrauterine device
IUS	Intrauterine hormone-releasing system
LPLV	Last Participant Last Visit
MAAE	Medically Attended Adverse Events
MHRP	U.S. Military HIV Research Program
MOP	Manual of Procedures
MPLA	Monophosphoryl lipid A
NAAT	Nucleic Acid Testing
NCO	Non-commissioned officer
NHP	Non-human primate
NK	Natural Killer Cell
NKT	Natural Killer T cell
NSAIDs	Nonsteroidal anti-inflammatory drugs
OAE	Other significant adverse events
OHARO	Office of Human and Animal Research Oversight
OHRO	Office of Human Research Oversight
ORA	Office of Regulated Activities
PBMC	Peripheral blood mononuclear cell
PI	Principal Investigator
PIMMCs	Potentially Immune-Mediated Medical Conditions
PIN	Participant identification number
PRB	Protocol Review Board
PSRT	Protocol Safety Review Team
PSSO	Product Safety Surveillance Office
PVG	Pharmacovigilance
RFADCC	Rapid and fluorometric ADCC
SAE	Serious adverse event
SD	Standard deviation
SGTP	Serum glutamic pyruvic transaminase
SOE	Schedule of Evaluations
SOP	Standard operating procedure
STI	Sexually transmitted infection

Abbreviation or Specialist Term	Explanation
TOU	Test of understanding
UPIRTSO	Unanticipated problems involving risks to subjects or others
USAMRDC	United States Army Medical Research and Development Command
WRAIR	Walter Reed Army Institute of Research

1. PROTOCOL SUMMARY

1.1. Synopsis

Name of Sponsor: The Surgeon General, Department of the Army	
Name of Investigational Product: A244, B.63521, and ALFQ	
Name of Active Ingredient: A244 consists of the gp120 envelope glycoprotein HIV-1 subtype CRF_01E A244 derived from the CM244 CRF_01AE. The A244 gp120 envelope has an 11 amino N-terminal deletion, similar to the A244 protein used in AIDSVAX B/E. B.63521 gp120 is a recombinant HIV-1 Env protein containing an 11 amino acid truncation at the N-terminus of gp120 that enhances antigenicity and immunogenicity. ALFQ (Army Liposomal Formulation) is a liposomal adjuvant containing a synthetic monophosphoryl lipid A (MPLA) with the addition of QS-21.	
Protocol Number(s): RV 575	
Title of Study: A Phase 1, Randomized Study to Evaluate the Safety, Tolerability, and Immunogenicity of Ranging Doses of ALFQ Adjuvant in a Candidate HIV Vaccine Containing A244 and B.63521	
Study Site(s): WRAIR Clinical Trials Center (CTC)	
Principal Investigator: MAJ [name], MTM&H *Protocol Team Roster included as Attachment 1 .	
Studied Period (years): Estimated date first participant enrolled: May 2022 Estimated date last participant completed: October2023 Study duration: Specimen analysis and monitoring of medically attended adverse events (AEs) will continue 12 months beyond the final participant vaccination. Anticipated end date is October 2028.	Phase of Development: Phase I
Objectives: Primary: To evaluate the safety and tolerability (including reactogenicity) of candidate vaccine A244/B.63521 (300 µg each) with ALFQ adjuvant at the 200 µg, 100 µg, and 50 µg doses Secondary: To evaluate the effect of candidate vaccine A244/B.63521 (300 µg each) with ALFQ adjuvant at the 200 µg, 100 µg, and 50 µg doses on cellular, and humoral immune responses Exploratory: To characterize B-cell functional specificities for each vaccination regimen To characterize innate immunity To assess the innate/gene expression induced across vaccination regimens To perform systems serology analyses	

Name of Sponsor: The Surgeon General, Department of the Army
 
To characterize the impact of vaccination with the ALFQ adjuvant on the permissiveness and expression to in vitro HIV infection of CD4+ T cells and differentiated macrophages


Endpoints
 
Primary
 
Evaluate the occurrence and severity of solicited local and systemic AEs following candidate vaccine administration.
 
Evaluate the occurrence, severity, and relationship to vaccination of unsolicited AEs after candidate vaccine administration.
 
Evaluate the occurrence of SAEs, and new-onset medical conditions.
 
Evaluate the occurrence of AEs of special interest (AESIs) following candidate vaccine administration.
 
Secondary
 
Compare plasma Immunoglobulin G (IgG) binding antibodies to gp120 in terms of magnitude, durability, and area under the curve among groups with differing ALFQ doses.
 
Characterize and assess the magnitude of cell-mediated immune responses elicited across vaccination regimens including antigen -specific CD4 and CD8 T cell responses and polyfunctionality.
 
Exploratory
 
Characterize plasma IgG and Immunoglobulin A (IgA) binding antibodies to HIV gp120, neutralizing antibodies, and non-neutralizing effector functions such as Antibody-Dependent Cell-Mediated Cytotoxicity (ADCC) and Antibody-Dependent Cell-Mediated Phagocytosis (ADCP) with emphasis on RV144 immune correlates of risk of HIV acquisition.
 
Characterize B-cell functional specificities for each vaccination regimen by quantifying antigen-specific responses through B-cell Enzyme-Linked Immunospot (ELISPOT), phenotyping the magnitude and activation status of B cell subsets via flow cytometry and isolation of monoclonal antibodies from selected vaccine recipients.
 
Characterize innate immunity through quantification of soluble chemokines and cytokines and assessing the phenotype and function of cellular innate immune subsets such as Natural Killer Cell (NK), NKT, and dendritic cells.
 
Characterize effects of host genetic polymorphisms on immune responses and characterize differentially expressed genes.
 
Characterize the impact of vaccination with the ALFQ adjuvant on the permissiveness and expression to in vitro HIV infection of CD4+ T cells and differentiated macrophages through integrated HIV-DNA PCR, cell associated-DNA and RNA, flow cytometry of various activation markers and HIV Gag protein, ELISA of HIV p24 in the cell culture supernatant, and production of cytokines/chemokines.


Methodology
 
This study is exploratory in nature.
 
The purpose of this study is to optimize ALFQ dosing. We will also evaluate the B.63521 protein. Safety will be assessed through the frequency of the overall and specific post-vaccination reactions. Blood will be collected to assess humoral, cell-mediated, and innate immune responses.
 
Healthy adults not living with HIV, who are available for 14 months will be enrolled. A total of 60 participants will be enrolled in one of three arms, each comprised of 20 candidate vaccine recipients. Each arm will receive identical doses of A244 and B.63521 (300 micrograms of each protein). In

Name of Sponsor: The Surgeon General, Department of the Army

addition, Arm 1 will receive 200 micrograms of ALFQ. Arm 2 will receive 100 micrograms of ALFQ. Arm 3 will receive 50 micrograms of ALFQ. The safety, reactogenicity, and immunogenicity will then be compared among the three arms to determine the optimal dose of ALFQ.
 
All vaccinations will be split into 2 half doses, which will be administered intramuscularly (IM) into the same deltoid muscle. Vaccinations will occur at months 0, 1, and 2. The second vaccination will be administered into the contralateral deltoid at study month 1 compared to the first vaccination at study month 0. The third vaccination at study month 2 will be administered into the same deltoid as the first vaccination at study month 0. Participants will be followed for 12 months following the last study vaccination.

Number of Subjects:
 
Maximum number of subjects to be screened: 150
 
Maximum number of subjects to be enrolled: 60


Inclusion Criteria
 
Potential participants are required to meet all of the following criteria for enrollment into the study.
 
1. Healthy adults between the ages 18-55 years (inclusive)2. Must be at low risk for HIV infection per investigator assessment and using the study risk assessment tool.3. Able and willing to provide written, informed consent4. Able and willing to comply with all research requirements, in the opinion of the Investigator5. Agreement to refrain from blood donation during the course of the study and within the 2 months prior to study entry6. Minimum body weight of 110 pounds (lbs) (50kg)7. Laboratory Criteria within 45 days before enrollment:
a. Hemoglobin \geq 11.7 g/dL for women; \geq 12.5 g/dL for menb. White Blood Cell count = 3,500-10,800 cells/mm³c. Platelets \geq 140,000/mm³ and \leq 450,000/mm³d. Alanine aminotransferase (ALT; SGPT) $<$ 1.25 x ULNe. Serum creatinine \leq 1.25 x institutional upper limit of the reference rangef. Negative HIV testing (HIV Ab / antigen 4th generation screen with reflex confirmatory RNA testing)g. Negative HBsAg and hepatitis C antibody testing8. Birth control requirements: 
Note: As above, Grade 1 lab abnormalities detected on screening may be repeated at PI discretion. Persistent Grade 1 abnormalities that are felt to represent the non-pathologic baseline for the subject will be documented before a subject is enrolled in the trial and are allowable per discretion of the PI.
 
All participants assigned female at birth must meet one of the following two criteria:
 
a. No reproductive potential due to post-menopausal status (12 months of natural [spontaneous] amenorrhea) or hysterectomy, bilateral oophorectomy, or tubal ligationb. People of childbearing potential should agree to practice highly effective contraception at least 30 days before enrollment and through 3 months post-last vaccination, using one of the following methods: condoms (male or female) with spermicide; diaphragm, or cervical cap with spermicide; intrauterine device; contraceptive pills, patch, injection,


Name of Sponsor: The Surgeon General, Department of the Army
 
intravaginal ring or other FDA-approved contraceptive method; male partner has previously undergone a vasectomy; abstinence
 
c. All participants are encouraged to engage in safe sex practices to prevent HIV acquisition
 
9. For all participants assigned female at birth, except those with a history of hysterectomy or bilateral oophorectomy, a negative β-HCG pregnancy test (urine) on the day of enrollment and each vaccination day is required. Because tubal ligations have a failure rate that is not insignificant, and because 12 months of spontaneous amenorrhea can be a result of polycystic ovarian syndrome and does not completely preclude pregnancy, a negative β-HCG pregnancy test at enrollment and on each vaccination day is also required for participants assigned female at birth with a history of either of these).
 
10. No plans to travel outside the Washington DC metro area (DC, Maryland, and Virginia) that would prevent compliance with planned study visits
 
11. Test of Understanding (TOU) (minimum passing score of 80% with 2 attempts permitted)


Exclusion Criteria
 
Potential participants meeting any of the following criteria will be excluded from enrollment.
 
1. Receipt of any investigational HIV vaccine or investigational adjuvant2. Received an investigational product in the 30 days before enrollment, or planned to receive during the study period. This does not include products with emergency use authorization.3. Concurrent participation in another clinical research study4. Any serious medical illness or condition5. Receipt of immunoglobulins or blood products within 3 months before enrollment6. Any history of anaphylaxis or allergy to study product7. History of sickle cell trait or disease8. Pregnancy, lactation, or intention to become pregnant during the study9. History of active/recent cancer still within treatment or active surveillance follow-up (except basal cell carcinoma of the skin and cervical carcinoma in situ). Treated/resolved cancers with no likelihood of recurrence may be deemed acceptable at Principal Investigator (PI) discretion.10. History of autoimmune disease11. History of Potentially Immune-Mediated Medical Conditions (PIMMCs)12. Suspected or known current alcohol or drug abuse as defined by an alcohol intake of greater than 3 drinks a day on average for a man, and greater than 2 drinks a day on average for a woman13. Any other significant disease, disorder or finding which may significantly increase the risk to the volunteer because of participation in the study, affect the ability of the volunteer to give informed consent, participate in the study, or impair interpretation of the study data, in the opinion of the Investigator14. History of splenectomy15. History of confirmed or suspected immunodeficiency16. History of hereditary angioedema (HAE) acquired angioedema (AAE), or idiopathic forms of angioedema

Name of Sponsor: The Surgeon General, Department of the Army


17. History of asthma that is unstable or required emergent care, urgent care, hospitalization, or intubation during the past 2 years
 
18. History of diabetes mellitus (type I or II), with the exception of gestational diabetes
 
19. History of thyroid disease (except for well controlled hypothyroidism)
 
20. History of idiopathic urticaria within the past year
 
21. History of hypertension that is not well controlled by medication or that is persistently greater than 140/95 at screening
 
22. History of bleeding disorder diagnosed by a doctor (e.g., factor deficiency, coagulopathy, or platelet disorder requiring special precautions) or significant bruising or bleeding difficulties with IM injections or blood draws
 
23. History of chronic or active neurologic disease to include seizure disorder and chronic migraine headaches. Exceptions are: i) childhood febrile seizures, or ii) seizures secondary to alcohol withdrawal more than 3 years ago
 
24. Subjects receiving any of the following substances:
 
a. Systemic immunosuppressive medications or cytotoxic medications within 12 weeks before enrollment [with the exception of a short course of corticosteroids (\leq 14 days duration or a single injection) for a self-limited condition at least 2 weeks before enrollment; inhaled, intranasal or topical steroids are not considered exclusionary]b. Treatment with known immunomodulators including allergy immunotherapy (other than nonsteroidal anti-inflammatory drugs [NSAIDs] or stable maintenance immunotherapy (doses not in the process of being increased), at the discretion of the Protocol Safety Review Team (PSRT)) for any reasonc. Live attenuated vaccines within 30 days before initial study vaccine administrationd. Medically indicated subunit, mRNA, or killed vaccines, e.g., influenza, pneumococcal, vaccines with QS-21 as an adjuvant, or allergy treatment with antigen injections, planned for administration 14 days before or after study vaccine administration 
25. History of arthritis diagnosis other than osteoarthritis
 
26. History of other diagnosed rheumatoid disorders
 
27. Has an acute illness or temperature \geq38.0 °C/100.4 °F on any study injection day or within 48 hours of planned study injection.
 
Note: Participants will not be excluded from further consideration for enrollment and study injections. Volunteers with fever or an acute illness on the day of study injection or in the 2 days before the study injection may be re-assessed by a study physician for resolution of the condition and enrolled and receive the study injection so long as the injection is within allowable windows. Military personnel will be excluded from participation in this study, regardless of leave status due to the potential for a false-positive HIV test result on mandatory HIV testing. This could have adverse effects on deployment status.
 
Final evaluation of eligibility will be based on the medical judgment of the investigator based on his/her medical and research experience.


Investigational Product, Dosage, and Mode of Administration

Arm 1: An injection containing A244/B.63521 with 200 µg of ALFQ adjuvant will be administered as an IM injection into the deltoid muscle at visits 1, 3, and 5 (corresponding to Day 1, Day 29, and Day 57).

Arm 2: An injection containing A244/B.63521 with 100 µg of ALFQ adjuvant will be administered as an IM injection into the deltoid muscle at visits 1, 3, and 5 (corresponding to Day 1, Day 29, and Day 57).

Arm 3: An injection containing A244/B.63521 with 50 µg of ALFQ adjuvant will be administered as an IM injection into the deltoid muscle at visits 1, 3, and 5 (corresponding to Day 1, Day 29, and Day 57).

Investigational Products

Products: A244, B.63521, and ALFQ

Dosage: 200 µg, 100 µg, and 50 µg of ALFQ (Dose of MPLA/3D-PHAD® component), **300 µg** A244, and **300 µg** of B.63521

Adjuvant: ALFQ (200 µg of MPLA/3D-PHAD® and 100 µg of QS-21 diluted in 0.5 mL Sorenson's buffer)

Total Volume: 1.8 mL

Mode and Location of Administration: IM injection into the same deltoid muscle (same side) for all injections.

Duration of Study Participation: Participants will receive IM administration of the investigational products at months 0, 1, and 2, after which they will be followed for 12 months after the 3rd injection for safety analyses. Total duration of participation will be 14 months.

Criteria for Evaluation:

Immunogenicity:

Humoral responses will be assessed by HIV-specific binding antibody assays, HIV-specific neutralizing antibody assays, and non-neutralizing antibody function assays.

HIV-specific cell-mediated responses will be assessed by intracellular cytokine staining, CD4 and CD8 T cell proliferation, and related assays. Innate immune responses and genetic responses will be quantified.

Safety:

Safety will be assessed both by direct physical examination and by diary cards, which serve as memory tools for better identification of reactions. Participants will be assessed at pre- vaccination baseline and will remain in clinic under direct observation for at least 30 minutes post vaccination. Participants will return to clinic post-vaccination to be assessed for symptoms of local and systemic reactogenicity. Results will then be compared among the three ALFQ dose arms.

Participants will be followed for a total of 12 months post final vaccination. Serious Adverse Events and SAEs will be recorded at all visits along with timing and possible attribution to Investigational Product. Because this clinical trial involves an adjuvant, Adverse Events of Special Interest AESIs and Medically Attended Adverse Events (MAAE) will also be assessed. Safety laboratory analyses of complete blood count, liver function tests, urinalysis, and pregnancy test in females will also be performed. Safety results will then be compared among dose arms.

Statistical Methods:

RV 575 is designed to optimize ALFQ dosing. The primary objective is to compare dose- dependent safety and reactogenicity of ALFQ. For safety analyses, the occurrence of local and systemic reactogenicity symptoms, AEs, and SAEs will be assessed as the proportions of participants experiencing such safety events and compared among the three study arms. The secondary objective is to assess immunogenicity.

1.2. Schema

The study design is illustrated in Figure 1.

Figure 1: Study Design

Number of participants (N) = 60		Vaccination schedule in months (days)		
	Number of participants (N)	Month 0 (Day 1)	Month 1 (Day 29)	Month 2 (Day 57)
Arm 1	20	300 μ g A244	300 μ g A244	300 μ g A244
		300 μ g B.63521 200 μ g ALFQ	300 μ g B.63521 200 μ g ALFQ	300 μ g B.63521 200 μ g ALFQ
Arm 2	20	300 μ g A244	300 μ g A244	300 μ g A244
		300 μ g B.63521 100 μ g ALFQ	300 μ g B.63521 100 μ g ALFQ	300 μ g B.63521 100 μ g ALFQ
Arm 3	20	300 μ g A244	300 μ g A244	300 μ g A244
		300 μ g B.63521 50 μ g ALFQ	300 μ g B.63521 50 μ g ALFQ	300 μ g B.63521 50 μ g ALFQ

1.3. Schedule of Activities

The detailed schedule of study events is provided in Table 1 and a summary of laboratory assessments is provided in Table 2.

Table 1: Schedule of Evaluations (SOE)

Visit Number	0	1	2	3	4	5	6	7	8	9	10 ² /Exit 4	Phone Follow-up #1	Phone Follow-up #2
Visit Type	Screen	V1	Safety & Immun	V2	Safety & Immun	V3	Safety & Immun	MAAE follow-up	MAAE follow-up				
Visit Day	-45 to -3	1	15	29	43	57	58-59	64	71	169	337	365	393
Window			± 3d	± 7d	± 3d	± 7d		± 3d	± 3d	± 7d	± 7d	± 7d	± 7d
Visit Week	0	2	4	6	8	8	9	10	24	48	52	56	
Clinical													
Briefing and Contact Information	X												
Informed Consent	X												
Test of Understanding	X												
Enrollment and Randomization		X											
Vaccination		X						X					
Vital Signs and Physical exam ¹	X	X	X	X	X	X	X	X	X	X	X	X	
Medical History & Concomitant Medications	X	X	X	X	X	X	X	X	X	X	X	X	

RV-575/WRAIR 2924 Protocol
IND 28352, S-21-03

The Surgeon General
Department of the Army

Visit Number	0	1	2	3	4	5	6	7	8	9	10 ² /Exit 4	Phone Follow-up #1	Phone Follow-up #2
Visit Type	Screen	V1	Safety & Immun	V2	Safety & Immun	V3	Safety & Immun	Safety & Immun	Safety & Immun	Safety & Immun	MAAE follow-up	MAAE follow-up	MAAE follow-up
Visit Day	-45 to -3	1	15	29	43	57	58-59	64	71	169	337	365	393
Window			± 3d	± 7d	± 3d	± 7d		± 3d	± 3d	± 7d	± 7d	± 7d	± 7d
Visit Week	0	2	4	6	8	8	9	10	10	24	48	52	56
Adverse Event Documentation (AE, SAE, AESI) ³		X	X	X	X	X	X	X	X	X			
Medically Attended Adverse Event (MAAE) Documentation ⁴	X	X	X	X	X	X	X	X	X	X	X	X	X
Diary Card		X	X	X	X	X	X	X	X				
HIV Risk Counseling	X	X	X	X	X	X	X	X	X	X	X	X	X
Pregnancy Test ⁷ & Pre/Post Counseling	X	X		X			X		X	X			
CBC w/ diff	4	4	4	4	4	4	4	4	4	4	4	4	4
Creatinine, ALT	4	4	4	4	4	4	4	4	4	4	4	4	4
Hepatitis B and Hepatitis C Serology	7.5												
HIV Testing*	7.5		7.5		7.5		7.5		7.5	7.5	7.5	7.5	7.5

Visit Number	0	1	2	3	4	5	6	7	8	9	10 ² /Exit 4	Phone Follow-up #1	Phone Follow-up #2
Visit Type	Screen	V1	Safety & Immun	V2	Safety & Immun	V3	Safety & Immun	Safety & Immun	Safety & Immun	Safety & Immun	MAAE follow-up	MAAE follow-up	MAAE follow-up
Visit Day	-45 to -3	1	15	29	43	57	58-59	64	71	169	337	365	393
Window			±3d	±7d	±3d	±7d		±3d	±7d	±7d		±7d	±7d
Visit Week	0	2	4	6	8	8	9	10	24	48	52	56	
Research⁵													
HIV Binding Antibody		SP	SP	SP	SP	SP	SP		SP	SP	SP	SP	
HIV Neutralizing Antibody Assays		7.5	7.5	7.5	7.5	7.5	7.5		7.5	7.5	7.5	7.5	
Functional Antibody Assays		SP	SP	SP	SP	SP	SP		SP	SP	SP	SP	
B-Cell Analysis		17	17	17	17	17	17		17	17	17	17	
Multiparameter Flow Cytometry		17	17	17	17	17	17		17	17	17	17	
Innate Cell Analysis		17	17			17			17	17	17	17	
Transcriptomics		2.5	2.5	2.5	2.5	2.5	2.5		2.5	2.5	2.5	2.5	
Additional Immunogenicity Testing		42.5	8.5	8.5	8.5	8.5	8.5		17	25.5	34	34	

Visit Number	0	1	2	3	4	5	6	7	8	9	10 ² /Exit 4	Phone Follow-up #1	Phone Follow-up #2
Visit Type	Screen	V1	Safety & Immun	V2	Safety & Immun	V3	Safety & Immun	Safety & Immun	Safety & Immun	Safety & Immun	MAAE follow-up	MAAE follow-up	MAAE follow-up
Visit Day	-45 to -3	1	15	29	43	57	58-59	64	71	169	337	365	393
Window			± 3d	± 7d	± 3d	± 7d		± 3d	± 3d	± 7d	± 7d	± 7d	± 7d
Visit Week	0	2	4	6	8	8	9	10	24	48	52	56	
Daily Volume (mL) ⁶	23	111.5	85	60.5	85	60.5	19.5	70.5	102	100	108		
Cumulative Volume (mL)	23	134.5	219.5	280	365	425.5	445	515.5	617.5	717.5	825.5		
8-Week Cumulative Volume (mL)						402.5	422	381	483	100	108		

SP = Assay performed from stored plasma; no additional blood volume required

¹ Full physical examination at screening (visit S1) and targeted physical examination at all other visits; Vitals to be collected both pre- and at about 30 minutes post-vaccination at Visit Day 1, 29, and 57.

² Participants will be contacted for the unblinding visit after the clinical data is locked.

³This includes unsolicited AEs which will be collected until 28 days post each vaccination.

⁴Medically Attended AEs will be followed through the end of the study, a full 12 months following the last vaccination. After clinic visits end, follow-up for MAAEs will occur by monthly phone calls for two months.

For those participants who are unable to continue participation in the study, but who do not withdraw consent, an exit visit will be conducted.

⁵ Research labs may be performed at any visit where sufficient stored samples are available

⁶ Blood volumes for clinical lab assays may be adjusted as long as maximum daily blood volume is not exceeded.

⁷ Pregnancy tests can be conducted at any visit if clinically indicated.

⁸ Any clinically indicated safety labs can be obtained at investigator discretion

^{*}10 mL EDTA verification blood collection for HIV incident case resolution for enrolled participants.

^{**}Blood will be collected into vacutainer tubes according to standard operational procedures. Substitution of tube types may be made as long as the substitution does not interfere with the study performance. A 10% variance in blood volume is acceptable, such as in the case of an error or a broken or clotted vial.

Table 2: Protocol-Required Safety Laboratory Assessments

Laboratory Assessment	Parameters ^a
Hematology	CBC with differential
Clinical Chemistry	Creatinine, ALT
Laboratory Assay	HIV

^a Acronyms

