4.7. End of Study Definition

The end of the study primary completion date is defined as the last subject last visit (LSLV). Each participant will be followed for 12 months after the final vaccination. Follow up includes 10 months of clinic visits and two additional telephone follow up visits at 1-month intervals for a total of 12 months. The completion of laboratory assays and data analysis is anticipated to take up to 5 years from the primary completion date.

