8.2.1.5. Medically Attended Adverse Events (MAAE)

The FDA requests that clinical trials of preventive vaccines with adjuvants such as ALFQ provide for collection and analysis of data relating to MAAEs among subjects in all treatment groups through 12 months or longer following the last study vaccination, due to the theoretical potential for induction of autoimmune or auto-inflammatory diseases.

MAAEs are defined as AEs with medically attended visits including hospital, emergency room, urgent care clinic, or other visits to or from medical personnel for any reason. Adverse events (e.g., abnormal vitals) identified at a routine study visit will not be considered MAAEs. MAAEs include, but are not limited to, PIMMCs.

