8.2.2. Timeframe for Collecting Adverse Event Information

All AEs and SAEs will be collected from the start of treatment until the end of the protocol-defined follow-up period, at the time points specified in Section 1.3, Schedule of Activities. Adverse events and SAEs will be assessed at all study visits, documented in the source records, and recorded on the CRFs using accepted medical terms and/or the diagnoses that accurately characterize the event. All unsolicited AEs will also be collected from at least 28 days after each vaccination. Medical occurrences that begin before the start of study treatment but after obtaining informed consent will be recorded on the Medical History/Current Medical Conditions section of the CRF.

Unsolicited adverse events (AEs) and Medically Attended Adverse Events (MAAEs) will be collected from the day of IP administration and for the next 28 days. The investigator will also document SAEs, MAAEs and AESIs (including PIMMCs) for at least 12 months after subjects receive their last study vaccination.

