## 5.5. Missing and Outlier Data

All attempts will be made to collect all data per protocol. Frequencies of missingness for primary outcomes will be calculated overall and within each study group. Less than 10% missing data that are missing completely at random will be considered ignorable missingness and complete case analysis will be utilized. No imputation will be performed for missing values. Data visualizations such as boxplots, histograms, or scatter plots will be used to identify outliers. Single outliers may be identified if values are outside of 1.5x the interquartile range depending on normality assumptions. Outliers will not be excluded from the primary analyses. Outliers identified during the analysis will be discussed in the analysis report.

Measurements that occur outside of study visit windows may be considered missing in sensitivity analyses. Table S5 provides an overview of each study visit along with the visit window upper and lower bounds, as specified in the study protocol.

Table S6. Analysis Time Windows

Visit	Visit day (visit window in days)	Lower bound (days)	Upper bound (days)
Screen	-45 to -3	-45	-3
Visit 1 (V1)	1	1	1
Visit 2 (Safety & Immun)	15 ( $\pm 3$ )	12	18
Visit 3 (V2)	29 ( $\pm 7$ )	22	36
Visit 4 (Safety & Immun)	43 ( $\pm 3$ )	40	46
Visit 5 (V3)	57 ( $\pm 7$ )	50	64

Visit	Visit day (visit window in days)	Lower bound (days)	Upper bound (days)
Visit 6 (Safety & Immun)	58-59	58	59
Visit 7 (Safety & Immun)	64 ( $\pm 3$ )	61	67
Visit 8 (Safety & Immun)	71 ( $\pm 3$ )	68	74
Visit 9 (Safety & Immun)	169 ( $\pm 7$ )	162	176
Visit 10 /Exit 4 (Safety & Immun)	337 ( $\pm 7$ )	330	344
Phone Follow-up 1 (MAAE)	365 ( $\pm 7$ )	358	372
Phone Follow-up 2 (MAAE)	393 ( $\pm 7$ )	386	400

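### After an in-window third dose, the last scheduled safety contact comes about 48 weeks later, short of the 12-month minimum that the protocol states

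*Protocol*

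**What the plan says.** The commitment appears in several places, each worded as a minimum:

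- **Protocol Section 1.3, Table 1 footnote 4:** MAAEs are followed to the end of the study, "a full 12 months following the last vaccination". The SAP's schedule of events (Section 4.1) carries the same footnote.
- **Protocol Section 8.2.2:** "The investigator will also document SAEs, MAAEs and AESIs (including PIMMCs) for at least 12 months after subjects receive their last study vaccination".
- **Protocol Section 8.2.1.5:** the FDA is said to ask for MAAE data "through 12 months or longer following the last study vaccination", because an adjuvant of this kind could in theory induce autoimmune or auto-inflammatory disease.

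Protocol Section 4.7 explains how the period is built: "Follow up includes 10 months of clinic visits and two additional telephone follow up visits at 1-month intervals for a total of 12 months".

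The schedule is the same in Protocol Table 1 and SAP Table S6 (SAP Section 5.5). Dose 3 is on Day 57, window Day 50 to 64. The last clinic visit is on Day 337. The two phone contacts are on Day 365 and Day 393, and the window of the second is Day 386 to 400. Both phone contacts are labelled as MAAE follow-up.

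**The concern.** A site that keeps exactly to the schedule makes its last contact about a month before a calendar year has passed since dose 3. The plan would then miss its own stated minimum through its design, with no deviation by anyone.

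The end of this period is what matters. The protocol gives late immune-mediated disease as the reason for the 12 months, and AESI occurrence is a primary safety endpoint. A condition that first appears between the last call and the anniversary of dose 3 has no scheduled contact at which it would be picked up. A report that describes follow-up as 12 months would overstate what was observed.

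**Working it through.** **Inputs** (Protocol Table 1; SAP Table S6): dose 3 on Day 57, window 50–64; Phone Follow-up #2 on Day 393, window 386–400; last clinic visit on Day 337.

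**1. Reproducing the plan's 12 months.**
- Clinic follow-up after dose 3: 337 − 57 = 280 days = 10 × 28.
- Two phone intervals: 365 − 337 = 28 and 393 − 365 = 28.
- Total: 393 − 57 = 336 days = 12 × 28 = 48 weeks.

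Section 4.7's ten months plus two is therefore exact if a month is 28 days. The 14 months of participation fit as well: 14 × 28 = 392 days, from Day 1 to Day 393. In calendar months (30.4375 days), 336 days is 11.04.

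**2. Nominal shortfall against a year.** 365 − 336 = 29 days, and 29 / 365 = 8%.

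**3. Range within the windows.** The documents do not say whether the calls are timed from Day 1 or from the actual dose 3, so both are shown.

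| Timing of the final call | Shortest | Longest | Shortfall from 365 |
|---|---|---|---|
| Fixed to study day | 386 − 64 = 322 | 400 − 50 = 350 | 15 to 43 days |
| Counted from actual dose 3 | 336 − 7 = 329 | 336 + 7 = 343 | 22 to 36 days |

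No cell reaches 365.

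**4. Whether the month labels are consistent.** Protocol Section 4.7 counts the Day 337 visit (week 48) as ten months after the last dose. SAP Section 8.1 calls week 48 twelve months post final vaccination. The same visit carries two different durations from the same dose, so a reader cannot recover one convention from the text.

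**5. Where a full year would fall.** For a dose on Day 57, 57 + 365 = Day 422. For doses on Day 50 and Day 64 it is Day 415 and Day 429. This matters for the remedy, because 422 − 365 = 57 days would then separate the two calls if only the second were moved. Day 429 also passes 14 calendar months (14 × 30.4375 = 426 days).

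**The case against.** The strongest reply is that this is a month convention and not a slip. Figure 1 of the protocol maps Month 0, 1 and 2 to Day 1, 29 and 57, and the SAP repeats this. On that scale every duration in Section 4.7 fits. This explains how the schedule was built. It does not settle the point, because the mapping is given only for the vaccination days and is not extended to follow-up. Phrases such as a full 12 months, at least 12 months, and 12 months or longer read as a calendar year. The labels also disagree on week 48.

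Some stronger readings are tempting, but the documents do not support them:

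- **That all 60 participants fall short.** If the calendar from Day 1 is kept, someone whose last dose is dose 1 has 393 − 1 = 392 days. Someone who stops after dose 2 has nominally 393 − 29 = 364. Section 7.2.1 leaves follow-up after discontinuation of vaccination to the safety review team.
- **That a late dose 3 always shortens follow-up further.** This is true only if calls are fixed to study day. Table S6 lists Visit 6 as Day 58–59 although dose 3 may fall as late as Day 64, so strict study-day timing cannot hold for every later visit. A figure of 314 days (386 − 72) would also need the 15-day limit in Section 7.2 to run from nominal Day 57, which that section does not say.
- **That the report will contain 12-month AESI or MAAE rates.** SAP Section 7 and its table shells label no rate that way. The risk lies in how follow-up is described.
- **That the FDA request is breached.** Only the protocol's summary of it is available, and what was agreed is not shown.

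Section 8.2.17 follows SAEs and events of special interest to resolution even beyond the reporting period. That covers events already known, not new onsets after the last contact.

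**Conclusion.** The point stands for participants who receive dose 3 in window. Their last scheduled contact is nominally 336 days after that dose and at most 350, against a stated minimum of 12 months. The nominal gap is 29 days. The conclusion rests on reading 12 months as 365 days. It does not depend on how the calls are anchored, since both readings fall short.

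The quoted footnote covers MAAEs; the commitment for SAEs and AESIs is in Section 8.2.2. Because the calls are labelled for MAAEs only, scheduled ascertainment of SAEs and AESIs may end earlier, at the last clinic visit (nominally 280 days after dose 3). The columns of the schedule tables are not legible enough in the text available to settle this, so it is a question for the sponsor.

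The consequence is limited to about one month of late safety follow-up and the accuracy of its description. All arms share the schedule, so the comparison between doses is not biased by it, and power and alpha do not change.

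**What to change.** Reconcile the stated duration with the schedule in both documents. The places are Protocol Table 1 and its footnotes and Sections 4.7, 8.2.1.5 and 8.2.2; and in the SAP the schedule in Section 4.1, Table S6 and the disposition shell (Appendix 1, Table 1). There are two ways to do it, and the choice is the sponsor's:

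1. **Bring the contact to the commitment.** Time the existing final contact from the actual dose-3 date so that it meets the stated minimum. The wording on monthly call intervals and on 14 months of participation must change with it; editing one table row alone would create the new contradictions shown in step 5.
2. **Bring the commitment to the schedule.** State follow-up as 48 weeks (336 days) wherever 12 months is now claimed, report it that way, and say how this relates to the request described in Section 8.2.1.5.

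Under either choice, define the month used for follow-up, give week 48 a single label in Protocol Section 4.7 and SAP Section 8.1, and state whether SAEs and AESIs are collected at the phone contacts.

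The cost is small. No visit or sample is added: either one existing call comes later, or the stated duration becomes slightly less favourable. The edits touch several sections and need IRB review under Section 10.1.1. A later call may also require participants to be informed under that section. For participants whose follow-up has already ended, only accurate wording remains available.
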